5.4 Pre-TKA Study Visit

All subjects will have TKA surgery approximately 3 months after their screening DXA visit, depending on the surgery schedule. The osteopenic group must have screening data at least 4 weeks prior to but not more than 6 months before this visit. The osteoporotic group must have received at least 8 weeks of ABL prior to this visit. Such variability is acceptable as this reflects clinical care and the primary comparison is BMD change from immediately prior to surgery to 15 months after TKA. As the usual wait time for surgery scheduling in our facility is ~2 months, this should not present a major impediment to study recruitment. The week prior to their scheduled TKA surgery all subjects will return to the OCRP and have repeat lumbar spine, bilateral femur/hip (including distal femur), forearm, PA & bilateral knee and total body DXA measurement, BIS, blood collection and adverse event assessment. Calcium and vitamin D₃ will be dispensed as appropriate. Additionally, subjects will be questioned regarding adverse events, falls and fractures; a physical exam or VFA may be performed if indicated per an investigator. If surgery is delayed for any reason, the study physician will determine if study continuation is appropriate and adjust the study visit timeline as necessary, this may include repeating laboratory tests and/or DXA exams.

5.5 6-month

All subjects will return to the OCRP for DXA (lumbar spine, bilateral femur/hip (including distal femur), forearm, total body, PA & lateral knee), BIS measurement and blood collection. Subjects will be questioned regarding adverse events, falls and fractures and PRO questionnaires will be completed; a physical exam or VFA may be performed if indicated per an investigator. Calcium and vitamin D will be dispensed as needed.

5.6. 15-month

All subjects will return to the OCRP for DXA (lumbar spine, bilateral femur/hip (including distal femur), forearm, PA & lateral knee and total body), BIS measurement and blood collection. Subjects will be questioned regarding adverse events, falls and fractures and PRO questionnaires will be completed; a physical exam or VFA may be performed if indicated per an investigator.

5.7 DXA Knee Precision

As PA and lateral knee bone density measurement is a new method, some assessment of technique reproducibility is indicated. The field standard is to acquire replicate scans by the same technologist in 30 subjects with repositioning in between. This will be acquired in 30 subjects volunteering for these additional scans at either the 6 or 15 month visit. A subject cannot volunteer to have this procedure twice, and one technologist will be identified to perform all scans.

5.8 Study participant recruitment and retention

Subjects will be recruited through the UW Total Joint Program and referred to the study at the time of their TKA consultation visit. Clinic staff will notify patients of the study and give them contact information to the OCRP study staff. Preliminary eligibility will be assessed via phone, and a screening visit scheduled as appropriate. To engage the untreated osteopenic group, we propose to share their 15-month post TKA BMD data.

5.9 Subject Discontinuation or Early Termination

Subjects will be informed that they have the right to withdraw from study participation at any time for any reason without prejudice to their medical care. The Investigator must withdraw subjects for the following reasons:

- Hypercalcemia (two consecutive measurements of > 10.5 mg/dL) that persists despite ABL dose reduction.
- Severe hypersensitivity to abaloparatide
- Inability to complete study procedures
- Lost to follow-up

The Investigator may withdraw subjects for any of the following reasons:

- Serious adverse events
- Non-compliance or protocol violations
- Incident vertebral or non-vertebral fragility fracture
- Other situations that may harm subjects or compromise study integrity

All subjects withdrawn prior to completing the study should be encouraged to have study procedures scheduled for the Month 15 visit as deemed appropriate by the PI. Subjects who discontinue or are withdrawn from the study will not be replaced.

6.0 STUDY PROCEDURES

6.1 DXA and BIS performance

Lumbar spine, bilateral femur/hip, forearm, total body and VFA DXA will be performed in the routine clinical manner per ISCD best practice recommendations using a Lunar iDXA (GE Healthcare). Prior to DXA, height will be measured with a wall-mounted stadiometer and weight with a calibrated analogue scale. Distal femur measurements will be obtained as described in prior work by Blaty et. al.²³ Briefly, the AFF feature of the Lunar enCORE software will be used to acquire a full femur DXA scan that starts at the proximal end of the tibia and continues beyond the greater trochanter. The DXA software is used to measure femur length and distances at 15%, 25% and 60% are calculated. Marker lines are then drawn 1 cm beyond each calculated distance and the top of a 2 cm ROI is placed at this point, thereby centering the ROI around 15%, 25% and 60% regions on the femur. Additionally, cortical width measurements of a 0.25mm cross-section will be extracted at each of these 3 defined points to evaluate changes in cortical thickness. Standard clinical DXA results will be shared with participants at screening, 15-month and early termination visits. Correspondence with primary health care providers and/or UW Total Joint Program staff will occur per subject preference. Additionally, PA & lateral bilateral knee scans will be acquired to determine utility of this technology in pre-surgical bone health assessment and post-surgical evaluation of skeletal change. Specific acquisition and analysis approaches will be determined based on available literature²⁴⁻²⁶

Bioimpedance spectroscopy (BIS) will be performed using the ImpediMed Imp SFB7 Body Composition Analyzer to assess body composition, as described in prior studies.⁴² This is a commercially available FDA approved device to measure body composition used in research, typically not in a clinical application. Briefly, subjects will lay on their back and adhesive tabs (leads) are placed on their hands and feet to connect cables leading to the BIS instrument, which will deliver small constant current, typically 200 uA RMS, with in the frequency range of 4 kHz to 1000 kHz sequentially, between two current electrodes spanning the body. Various leads placement combinations will generate fat free body composition measurements of the whole body and segmented arms and legs.

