2.1 Primary Study Endpoints

Specific Aim 1: To estimate the amount of distal femur bone loss in ABL treated osteoporotic patients 15 months post TKA and to compare the bone loss to the bone loss seen in untreated osteoporotic patients 12 months following TKA as reported by the meta-analysis of Prince et.al.³⁹ The limitation of this design is the comparison to a historic control rather than a control arm in this study. The reason this design was chosen is because it would be unethical to not offer treatment to newly diagnosed osteoporotic patients. Therefore, randomization to a control arm is not possible. Furthermore, based on our recent clinical experience we believe the rate of patient choice to refuse treatment will be quite low making recruitment of a non-randomized osteoporotic control arm futile. This reflects a dramatic change in osteoporosis care within orthopedic surgical practice at UW within the past year. Lastly, it is well documented that bone loss will occur in this patient population following TKA as seen in the multiple studies summarized in the Prince article.

Specific Aim 2: To estimate the amount of distal femur bone loss in untreated osteopenic patients 15 months post TKA.

The hypothesis for this aim is that TKA will significantly reduce BMD from baseline to 15 months post surgery in osteopenic patients. To assess this we will conduct a single arm pre-post observational study.

This design was chosen because data in the literature is sparse for BMD levels pre and post TKA in an osteopenic population. Collection of these data could demonstrate significant reduction in BMD following TKA which would lead to the justification of a future prospective study comparing a bone loss mitigating treatment to no treatment (current standard of care) in osteopenic TKA patients.

Specific Aim 3: To compare the amount of bone loss in ABL treated osteoporotic patients to untreated osteopenic patients 15 months following TKA.

The hypothesis for this aim is that the percent decrease from baseline in BMD at 15 months post TKA will be greater in the untreated osteopenic group compared to the treated osteoporotic group.

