It is understood these groups differ at baseline in BMD, but the belief is that after TKA the osteopenic group will become similar to the treated osteoporotic group. This is an exploratory analysis, and as such we may be under-powered to detect a significant effect. If trends in the differences are seen, and osteopenic patients are becoming osteoporotic after TKA, this would further bolster the need for future treatment studies in the osteopenic population.

2.2 Secondary Endpoints/Secondary aims:

- Distal femoral BMD change at the 15% and 60% ROIs
- Femur cortical thickness change at the 15%, 25% and 60% femur ROIs
- Trabecular bone score (TBS) assessment by Texture Research Investigation Platform (TRIP) software change at the 15%, 25% and 60% femur ROIs
- Patient reported outcomes; KOOS JR (knee function score), VR-12 (Veterans RAND 12 Item Health Survey) and Forgotten Joint Survey
- Precision of custom knee regions of interest
- Body composition and lean mass change
- TKA complications, e.g., revision surgery, fracture, etc

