4.2 Participant recruitment and study design

Study participants will be recruited from the UW Total Joint Program at the American Center. Patients expressing interest in study participation at the time of TKA scheduling will subsequently be contacted by a University of Wisconsin Osteoporosis Clinical Research Program (OCRP) study coordinator. Those expressing study interest will be scheduled at the OCRP where, following informed consent, medical history, collection of FRAX risk factors and a screening DXA of the lumbar spine, bilateral femurs/hips and VFA will be performed.

The overall study design is noted in Figure 1. Briefly, study eligibility will be determined by DXA. Those with osteoporosis who elect ABL will make up the treatment group ($n = 29$). An equal number ($n = 29$) will be recruited into the untreated group, i.e., those with osteopenia and no prior fragility fracture.

At screening, all participants will have a physical examination and blood collected for a metabolic panel, 25(OH)D and parathyroid hormone (PTH) measurement with additional sample to bank for potential future testing related to bone metabolism. Additionally, calcium and PRO questionnaires will be collected consisting of the KOOS JR, VR-12, and Forgotten Joint Survey. Subjects will be advised on how to achieve a daily calcium intake of 1,000-1,200 mg through food plus supplements, if needed, and up to 4000 IU of vitamin D₃ daily (as noted below; section 5.1). Subsequently, for those meeting all inclusion/exclusion criteria, ABL will be initiated in the treatment group approximately 3 months (depending on the surgery schedule) prior to their TKA and serum calcium will be assessed after one month of dosing. Subsequently, all subjects will have lumbar spine and bilateral femur DXA repeated within two weeks prior to TKA (± 7 days from the month -0.25 study visit) and again 6 and 15 months post TKA. At these same visits, PRO questionnaires will be administered and blood will be collected for serum banking.

Figure 1: Study Design Schematic

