4.3 Inclusion Criteria

1. Post-menopausal women and men age ≥ 55 years and scheduled to undergo primary TKA at the University of Wisconsin Total Joint Program.
2. Osteoporosis, i.e., BMD T-score (using female reference data) ≤ -2.5 at the lumbar spine, femoral neck OR total hip or ≤ -1.1 with VFA confirmed vertebral fracture or history of low-trauma nonvertebral fracture in the past 5 years OR osteopenia, BMD T-score (using female reference data) -1.1 to -2.4 at the lumbar spine, femoral neck or total hip and no prior low-trauma fracture.
3. Serum calcium (albumin-corrected), serum creatinine and PTH values all within the normal range and $25(\text{OH})\text{D} > 10 \text{ ng/mL}$.
4. Willing to supplement with daily calcium and/or vitamin D_3 at protocol specified doses.
5. Able to provide written informed consent.

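### No text provides for review or disclosure of the pre-surgery and month 6 spine and hip T-scores, so an untreated participant who crosses into osteoporosis could wait 9 months or more to be told

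*Combined protocol and SAP*

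**What the plan says.** Spine, femoral neck and total hip T-scores decide which group a participant enters. Section 4.3 defines the untreated group as "OR osteopenia, BMD T-score (using female reference data) -1.1 to -2.4 at the lumbar spine, femoral neck or total hip and no prior low-trauma fracture". The lower end of that range is next to the -2.5 cut-off for osteoporosis.

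The same sites are scanned again in everyone. Section 4.2 says "all subjects will have lumbar spine and bilateral femur DXA repeated within two weeks prior to TKA", and again at 6 and 15 months after surgery. Sections 5.4 and 5.5 and Table 1 agree.

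Section 6.1 says when results go to participants: "Standard clinical DXA results will be shared with participants at screening, 15-month and early termination visits". Section 5.8 is consistent with that: "To engage the untreated osteopenic group, we propose to share their 15-month post TKA BMD data". The next sentence of 6.1 allows correspondence with outside clinicians if the participant wishes, without stating timing or content.

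At the 6-month visit (5.5), "Subjects will be questioned regarding adverse events, falls and fractures and PRO questionnaires will be completed". Table 1 lists medical history at screening only and has no medication item at any later visit. Section 8 has rules for dropout and loss to follow-up, and none for a participant who starts a bone drug.

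**The concern.** Section 2.1 explains the absence of a control arm by saying that "it would be unethical to not offer treatment to newly diagnosed osteoporotic patients". Section 5.1 acts on that premise at screening: a participant who qualifies as osteoporotic is offered a discussion of abaloparatide. Nothing comparable is written for a participant who enters as osteopenic and first reads -2.5 or below on a later study scan. Yet section 2.1 contemplates this event under Aim 3: "If trends in the differences are seen, and osteopenic patients are becoming osteoporotic after TKA". The study would hold a result that meets its own osteoporosis criterion, with no written step to look at it, tell the participant or offer a discussion.

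A second, smaller matter follows. Aim 2 estimates bone loss in untreated osteopenic patients, and section 1.0 says that bisphosphonates or teriparatide mitigate this loss. A participant who starts such a drug, for example after a fracture or through outside care, would be analysed as untreated, and the protocol's schedule has no item that would show it. Section 5.9 adds a route: "All subjects withdrawn prior to completing the study should be encouraged to have study procedures scheduled for the Month 15 visit", subject to the principal investigator's judgement. A month 15 BMD measured on drug could therefore enter Aim 2.

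**Working it through.** **1. Delay implied by the schedule.** Scan times are from Table 1 and sharing times from 6.1.
- Month 6 scan to month 15 result: 15 - 6 = 9 months.
- Pre-surgery scan (month -0.25) to month 15 result: 15 + 0.25 = 15.25 months.

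The second case needs a crossing between screening and surgery, usually about 3 months (5.4 allows 4 weeks to 6 months for the osteopenic group) and before any loss caused by the operation. It is the less likely of the two.

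**2. How many might cross.** The documents do not say. The losses in sections 1.0 and 3.1 are at the distal femur, while the diagnostic sites are spine and hip. For illustration only, assume that the lowest T-scores at entry are spread evenly over the osteopenic range (-1.05 to -2.45 before rounding). Assume also that the change at one repeat scan is normal with mean m and SD s. A reading of -2.5 means an unrounded value at or below -2.45.

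| m, s (assumed) | Share reading -2.5 or below | Of 29 | Also fell by at least 0.3 | Of 29 |
|---|---|---|---|---|
| 0, 0.1 | 2.9% | 0.8 | 0.03% | 0.0 |
| -0.1, 0.2 | 10.0% | 2.9 | 4.6% | 1.3 |
| -0.2, 0.3 | 17.5% | 5.1 | 13.4% | 3.9 |

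The 0.3 threshold is also assumed, and it does not cleanly separate real change from noise. With m = 0 and s = 0.3, 5.2% (1.5 of 29) still pass it. The table shows only that the number could be none or a few.

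**3. The plan's own Aim 2 figure.** Section 8.0 gives d = 0.65, n = 21, 80% power and 29 enrolled. For a two-sided one-sample t-test at 5%, power comes from the noncentral t distribution with n - 1 degrees of freedom and noncentrality d√n. At n = 21 it is 80.9%. Enrolment is 21/(1 - 0.265) = 28.6, rounded up to 29. Both figures reproduce.

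**4. Effect of unrecorded drug starts on Aim 2.** Section 3.1 reports mean losses of 0.14 g/cm² at 6 months and 0.16 at both 12 and 24 months. Taking 0.16 at 15 months, 0.14/0.16 = 87.5% of the loss has occurred by month 6. Assume that k of 21 start a drug at month 6 and lose no more afterwards, with the SD unchanged. The mean loss then shrinks by the fraction (k/21) × 0.125, and the effective d is 0.65 × (1 - k × 0.125/21).

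| k | Shrinkage | Effective d | Power |
|---|---|---|---|
| 1 | 0.6% | 0.646 | 80.4% |
| 2 | 1.2% | 0.642 | 79.9% |
| 4 | 2.4% | 0.635 | 79.0% |

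The number of starts is not in the documents, so k is an assumption.

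**5. If starters are excluded instead.** At d = 0.65, power is 78.7% with n = 20 and 76.4% with n = 19.

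**The case against.** The strongest reply is that the text does not say "only". Section 6.1 commits to three sharing points and prohibits nothing earlier. Correspondence with providers has no visit limit. An investigator is involved at the pre-surgery and month 6 visits and may order an examination or VFA. Section 5.9 lets the investigator withdraw someone for situations that may harm them, and an early termination visit would bring a result. The participant also knows the screening T-score. All of this stands, so a reader who infers that the protocol withholds interim results, or that nobody will look at them, goes beyond the documents. The gap is the absence of a provision. What remains is that none of these routes is triggered by an interim T-score, and withdrawal ends participation.

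It is also fair that no spine or hip loss after TKA is given, that the Aim 3 remark is conditional and belongs to an exploratory aim, and that the ethical statement in 2.1 was written to justify the design. These points limit any claim about frequency. They do not remove the case of the single participant who crosses.

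On drug recording, a reader might infer that drug starts will go wholly unrecorded. That is not supported: the case report forms are not in the documents, section 7.0 leaves the collection tools to be designed, and a drug start could surface through the adverse event or fracture questions. The supported statement is narrower: the protocol schedule has no such item. Nor do the documents support a serious loss of power. Assuming that a drug cancels a participant's entire loss would give a much larger drop, but that cannot apply to month 6 starts when section 3.1 puts most of the loss before then.

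**Conclusion.** The concern holds as a gap in the protocol text. Interim spine and hip T-scores are measured without any stated review, disclosure or action. A qualifying month 6 reading could go undisclosed for 9 months, or about 15 months for the less likely pre-surgery reading. This rests on the schedule being followed as written. The number of participants affected is unknown, and every crossing rate above depends on assumed values.

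The statistical consequence is minor. Drug starts in the untreated group pull the Aim 2 loss toward zero, which is conservative for that aim's hypothesis. At month 6 they cost about 2 percentage points of power or less for up to 4 of 21. The stated sample size and power are not in error. The reason to act is participant safety, at low cost.

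**What to change.** - **Sections 5.4, 5.5 and 6.1:** have an investigator review the spine and hip T-scores at the pre-surgery and month 6 visits. If a reading of -2.5 or below is judged a real change, or a fragility fracture occurs, tell the participant promptly (and the provider, if the participant wishes), offer the treatment discussion of 5.1, and keep the participant in follow-up.
- **Table 1:** add an osteoporosis-drug question (drug and start date) at the pre-surgery, month 6 and month 15 visits.
- **Section 8:** keep participants in the group assigned at screening, report how many start a bone drug, and add one simple sensitivity analysis for Aim 2, such as repeating the test without those participants. A repeat scan to confirm a crossing, or a mixed model using only pre-drug BMD, is optional.

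The cost is a review of scans already taken, one question at three visits and a few lines of text. The downside is that a few informed participants may start treatment. With 2 of 21 starting at month 6, Aim 2 power is about 80% if they stay in the analysis and about 76% if they are excluded. That supports keeping them in the main analysis and using exclusion only as the sensitivity check. The disclosure and recording changes should be made together, because disclosure may prompt drug starts.

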6.2 Calcium/vitamin D

Calcium citrate, 500mg, will be provided to those needing supplementation to meet the 1000-1200 mg daily intake recommendation. Additionally, vitamin D₃ (cholecalciferol) 2000 IU will

be provided as needed per protocol section 5.1. Subjects will be allowed to supply their own supplements as long as they adhere to protocol dosing regimens.

6.3 ABL training

Study staff will train subjects in the treatment arm to administer ABL at the screening visit using the Radius ABL IFU, which will be given to subjects for reference. Study staff will review training at the time dosing starts either via tele/video communication or in person.

6.4 Laboratory

A comprehensive metabolic panel, calcium and PTH will be measured at the UW Clinical Laboratories per their standard clinical approach. Vitamin D research best practices require 25(OH)D measurements be performed using chromatography-based methodologies, consequently, 25(OH)D will be measured in the clinical laboratory using high performance liquid chromatography (HPLC).

7.0 DATA INTEGRITY

The OCRP research staff will ensure that appropriate approvals and documentation are in place per Federal and local requirements, including posting on clinicaltrials.gov. Additionally, they will design data collection tools, collect, clean and prepare all data for analysis by the statistician. In brief, data will be dually entered into Excel files, thus validating all entries. Ideally, dual-entry will be performed by different individuals; should it be necessary to have the same individual enter data, at least seven days will transpire between data entry cycles. Entry will then be compared and any discrepancy between entries will be corrected and validated.

